A randomized phase II trial will be used to compare the combination of Zotiraciclib (TG02) plus TMZ (selected from phase I) with TMZ alone in patients with recurrent grade III or IV malignant glioma. The TMZ alone arm will use the same dosing schedule as it is in the combination arm. The primary endpoint is progression free survival. We will enroll at least 10 patients and at most 40 patients for each arm at a rate of 4 patients per month. Patients will be equally randomized into two arms. Patients' KPS, MGMT promoter methylation status of the tumors and the presence of measurable disease at study entry will be used as stratification factors. We will follow all patients for at least 12 months, and monitor futility and toxicity as described below. We will use the methods described by Thall et al., to monitor progression-free survival (PFS), and we will stop enrolling patients early if, based on the available data, we have reason to believe that the median PFS of the Zotiraciclib (TG02) plus TMZ arm is less than that of the TMZ arm.^[50] Formally, we will stop enrolling patients early if

$$\Pr(\text{median PFS}_{\text{TG02+TMZ}} \geq \text{median PFS}_{\text{TMZ}} \mid \text{data from the trial}) < 0.78,$$

The futility monitoring will be conducted after enrolling 20, 40 and 60 patients (for two arms combined). Below are the operating characteristics of the above futility monitoring rule, assuming that the median PFS of the TMZ alone arm is 3 months.

Table 15 Operating Characteristics of the Futility Monitoring rule

	Median PFS for Zotiraciclib (TG02) +TMZ (months)				
	1	2	3	4	5
Early stop probability	0.999	0.812	0.374	0.170	0.097
Average sample size	23.7	42.1	62.6	70.9	74.7

Similar Bayesian methods will also be used to monitor the rate of DLT. We will monitor the two arms independently. Specifically, we will stop enrolling patients if the $\Pr(\text{DLT} > 35\% \mid \text{data}) > 0.9$. That is, we will stop enrolling patients if the data indicate that there is more than 90% chance that the true DLT rate is higher than 35%. This decision rule gives the following stopping rule, assuming a Beta (0.1, 0.4) prior distribution for DLT rate,

Stop enrolling pts if $[\# \text{ of pts with DLT}] / [\# \text{ of pts evaluated}] \geq 4/5, 6/10, 10/20, \text{ and } 15/30$.

Below are the operating characteristics of the toxicity monitoring rule.

Table 16: Operating Characteristics of the Toxicity Monitoring Rule

	True toxicity rate				
	0.2	0.3	0.4	0.5	0.6

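### The Phase II futility formula stops at a posterior probability below 0.78, which contradicts its own stated purpose and cannot produce Table 15; the complementary cut-off of 0.22 can

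*Combined protocol and SAP*

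**What the plan says.** Section 10.2 gives the futility rule three times: in words, as a formula and through its operating characteristics.

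- **Words.** Enrolment stops early if "we have reason to believe that the median PFS of the Zotiraciclib (TG02) plus TMZ arm is less than that of the TMZ arm".
- **Formula.** Introduced as the formal version, it stops enrolment if the posterior probability that the combination's median PFS is at least the control's is too low: "data from the trial}) < 0.78".
- **Operating characteristics.** "Table 15 Operating Characteristics of the Futility Monitoring rule" is presented as belonging to the rule just stated, "assuming that the median PFS of the TMZ alone arm is 3 months". For combination medians of 1, 2, 3, 4 and 5 months it reads "Early stop probability 0.999 0.812 0.374 0.170 0.097", with average sample sizes of 23.7, 42.1, 62.6, 70.9 and 74.7.

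The design settings are in the same section. Allocation is 1:1, with 10 to 40 patients per arm and accrual of 4 per month. On the timing of the looks it says: "The futility monitoring will be conducted after enrolling 20, 40 and 60 patients (for two arms combined"). Monitoring follows a cited event-time method (reference 50). No numerical prior or survival model for PFS is given.

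**The concern.** The words describe stopping when the combination looks worse. The formula demands much more: the trial continues only while there is at least a 78% posterior probability that the combination is as good or better. A posterior probability of 75% in favour of the combination would stop enrolment, although such data give no reason to think it inferior.

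This is the only comparison of PFS between the arms in Phase II that has a stated threshold and stated operating characteristics. The Statistical Analysis Plan text also names a log-rank test, but without an alpha or power. A statistician who programs the formula literally would usually end enrolment at 20 to 40 patients, even with a worthwhile benefit. One who follows the words or the table would depart from the rule labelled as formal. In both cases an early stop, or a failure to stop, could be challenged.

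**Working it through.** **Inputs (all section 10.2).** Control median 3 months; combination median 1 to 5 months; 1:1 allocation; 4 patients per month in total; looks at 20, 40 and 60 enrolled; maximum 80.

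**Step 1: what Table 15 implies about the first look.** Let p1, p2 and p3 be the probabilities of stopping at 20, 40 and 60 patients. In the equal-median column:

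- p1 + p2 + p3 = 0.374
- 60·p1 + 40·p2 + 20·p3 = 80 − 62.6 = 17.4

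Subtracting 20 × 0.374 = 7.48 from the second line leaves 40·p1 + 20·p2 = 9.92. Hence p2 = 0.496 − 2·p1 and p3 = p1 − 0.122. Neither can be negative, so 0.122 ≤ p1 ≤ 0.248. The rule behind Table 15 stopped between about 12% and 25% of equal-median trials at the first look.

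**Step 2: what each cut-off does at the first look.** With equal medians and the same prior in both arms, the posterior probability that the combination is at least as good is roughly uniform on 0 to 1. A cut-off of 0.78 therefore stops about 78% of trials at 20 patients, far outside the range in Step 1. A cut-off of 0.22 stops about 22%, which lies inside it.

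**Step 3: simulation over all looks.** The assumptions, needed because the plan gives no model, are exponential PFS, administrative censoring at each look, and a Gamma(a, b) prior on each arm's hazard. With d events and total follow-up T in an arm, the hazard has posterior Gamma(a + d, b + T). The median is ln 2 divided by the hazard, so

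Pr(median_E ≥ median_C | data) = Pr(F ≤ [(b + T_E)/(a + d_E)] / [(b + T_C)/(a + d_C)]),

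where F has 2(a + d_E) and 2(a + d_C) degrees of freedom. With 20,000 trials per cell, early-stop probability (average N) is:

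| Combination median (months) | Table 15 | 0.78 as written, vague prior | 0.22, vague prior | 0.22, prior worth 1 event per arm, centred on 3 months |
|---|---|---|---|---|
| 1 | 0.999 (23.7) | 1.000 (20.1) | 1.000 (23.2) | 0.999 (24.1) |
| 2 | 0.812 (42.1) | 0.995 (22.4) | 0.818 (41.0) | 0.806 (42.6) |
| 3 | 0.374 (62.6) | 0.923 (28.7) | 0.410 (60.2) | 0.372 (62.5) |
| 4 | 0.170 (70.9) | 0.779 (37.0) | 0.195 (69.8) | 0.167 (71.5) |
| 5 | 0.097 (74.7) | 0.623 (45.0) | 0.105 (74.1) | 0.087 (75.2) |

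The written rule does not reproduce Table 15. The last column matches every stopping probability to within 0.01 and every average sample size to within 0.6 patients.

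**Step 4: sensitivity.** The variants covered prior weight (vague to 3 events), accrual (2, 4 or 8 per month; fixed or Poisson), full follow-up, a Weibull shape of 1.3, progression seen only at 2-monthly scans, and a control median treated as known. With the same prior in both arms, the written rule stopped 91–95% of trials at 3 months, 65–85% at 4 months and 42–72% at 5 months.

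**The case against.** The strongest objection is that 0.22 is inferred rather than proved. The prior is unstated, and the cut-off that best fits Table 15 moves with it. With a vague prior, 0.20 fits better than 0.22: stopping 0.801 / 0.374 / 0.171 / 0.094 and average N 41.8 / 61.9 / 70.9 / 74.8 at 2 to 5 months. With a prior worth 3 events, 0.25 is also close (0.816 / 0.398 / 0.170 / 0.087). This stands: the arithmetic alone supports a region of about 0.20 to 0.25. Within that region, 0.22 is distinguished by being exactly 1 − 0.78, the value produced by writing the complement of the intended event.

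A prior strongly favouring the combination could in principle rescue 0.78. The only such prior that came near the stopping probabilities put the combination at about 12 months (3 prior events) and control at 3 months (5 prior events). It still missed the average sample sizes (32.1 against 23.7, and 48.8 against 42.1), and nothing in the documents supports it.

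The formula is a displayed equation read from PDF, so it should be checked against the typeset page. There is no sign of a misreading.

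Finally, the practical risk is tempered. The words and the table both point to the intended behaviour, the rule halts enrolment only, patients are still followed for at least 12 months, and section 10.1 indicates that Phase II has not begun. These points make harm less likely, but the formula is the version the plan calls formal.

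**Conclusion.** The formula is wrong as written. It contradicts the sentence that introduces it and the table said to describe it. Followed literally, it would stop about 92% of trials with no difference and, with a vague prior, about 78% and 62% of trials in which the combination raises median PFS from 3 to 4 or 5 months. Table 15 promises 37.4%, 17.0% and 9.7%.

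The percentages rest on exponential PFS and an assumed prior; the 5-month figure is the most sensitive. The contradiction does not rest on them: it persisted in every variant with a common prior, and the first-look bound comes from Table 15 itself. That the rule simulated was the complement (cut-off 0.22) is the most plausible explanation, subject to the sponsor's confirmation. This must be corrected before Phase II opens.

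**What to change.** Rewrite the rule so that enrolment stops if Pr(median PFS of the combination ≥ median PFS of temozolomide alone | data) < 0.22. Equivalently, enrolment stops if the posterior probability that the combination's median is the shorter exceeds 0.78. State the prior and survival model used for monitoring. Confirm from the simulation code that this rule and prior generated Table 15, and then keep the table.

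If 0.78 as written was really intended, replace Table 15 with that rule's own stopping probabilities and average sample sizes, and change the preceding sentence to say that enrolment continues only with at least 78% posterior probability that the combination is as good or better.

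The cost is one line of protocol wording and a statement of the prior, plus a short simulation re-run if the code is not at hand. No patients or study procedures are affected.

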6.3.4 Response Criteria

Response and progression will be evaluated in this study using the new proposed criteria Response Assessment in Neuro-Oncology Criteria (RANO) (see Appendix 15.5).[49]

Complete response: Requires all of the following:

- Complete disappearance of all enhancing measurable and non-measurable disease sustained for at least 4 weeks.
- No new lesions and stable or improved non-enhancing lesions (T2/FLAIR)
- Patient off steroids or on physiologic replacement only.
- Stable or improved clinically.

Partial response: Requires all of following:

- ≥ 50 % decrease compared to baseline (prior to treatment) in the sum of the products of perpendicular diameters of all measurable enhancing lesions sustained for at least 4 weeks;
- No new lesions and stable or improved non-enhancing lesions (T2/FLAIR).
- Patients off steroids or on physiologic replacement only.

- Stable or improved clinically.

Stable disease: Requires all of the following:

- Not complete response, partial response or progression.
- Stable non-enhancing lesions (T2/FLAIR).
- Patient on same or lower dose of steroids compared to baseline scan.

Progression: Requires any of the following:

- ≥ 25 % increase compared to baseline in the sum of the products of perpendicular diameters of enhancing lesions compared with the smallest measurement obtained either at baseline or best response with the patient on stable or increasing doses of steroids.
- Significant increase in T2/FLAIR non-enhancing lesions with the patient on stable or increasing doses of steroids (not caused by comorbid events e.g. Radiation therapy, demyelination, ischemic injury, infection, seizures, medication adverse events or changes in corticosteroid dose).
- Any new lesions.
- Failure to return for evaluation as a result of death or deteriorating condition or clear progression of non-measurable disease.

6.3.5 Patients will undergo response evaluations every 2 months.

- RANO criteria will be used to determine response and progression (includes CR, PR, SD and PD) **15.5**.
- Neurological exam.
- Performance status by Karnofsky Performance Status.

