Early stop probability	0.014	0.096	0.345	0.716	0.939
Average sample size	39.6	37.3	31.0	21.3	13.5

At progression, patients on the control arm will be offered treatment with Zotiraciclib (TG02) in combination with continued treatment with TMZ. If an effective salvage regimen, this may impact the secondary OS endpoint, but will not affect the primary endpoint of the study. The maximum number is 80 patients.

Statistical Analysis Plan

We will use descriptive statistics to summarize the demographic and clinical characteristics of patients. We will tabulate adverse events by grade by dose level and overall. For the cohort expansion and phase II component, we will estimate the proportion of patients with response with 95% exact binomial confidence intervals, and use descriptive statistics to summarize response duration. We will estimate PFS/OS with the Kaplan-Meier product limit estimator. Log-rank test will be used to compare the PFS/OS between Zotiraciclib (TG02)+TMZ and TMZ.

Changes of symptom burden (i.e., MDASI-BT) through study time points will be assessed by paired t-tests and linear mixed model. In the mixed model, subject-specific random intercept will be used to account for within-subject correlation, and measurement time will be included as a covariate. A sample size of 40 patients has 80% power to detect an effect size of 0.454 between time points using a two-tailed test with an alpha of 0.05. The two-sample t-test and linear mixed model will be used to evaluate differences in symptom burden using the MDASI-BT between Zotiraciclib (TG02) plus TMZ and TMZ. Cox proportional hazard model will be used to evaluate the relationship between MDASI-BT and disease progression. Logistic regression will be used to evaluate the relationship between MDASI-BT and tolerance to treatment.

Treatment effects will be evaluated by advanced MRI imaging study. Perfusion and diffusion – based MRI parameters, including but not restricted to blood volume, blood flow mean and median Apparent Diffusion Coefficient (ADC) value will be analysed. Results will be summarized. The mean and median value at different time points will be tabulated. Changes in such parameters will be analysed for statistical significance and correlate with the disease status.

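### Table 15's futility figures fit a simulation in which progression is known at once; the 8-weekly scan schedule is not reflected, and the printed cut-off must be reconciled first

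*Combined protocol and SAP*

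**What the plan says.** Section 10.2 sets the phase II size and pace: "We will enroll at least 10 patients and at most 40 patients for each arm at a rate of 4 patients per month". Allocation is equal ("Patients will be equally randomized into two arms") and the ceiling is stated at the end of the monitoring text: "The maximum number is 80 patients". On timing: "The futility monitoring will be conducted after enrolling 20, 40 and 60 patients (for two arms combined"). No minimum follow-up, minimum event count or pause in accrual is attached to a look.

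The printed rule stops enrolment when the posterior probability that the combination's median PFS is at least that of TMZ falls below 0.78 ("data from the trial}) < 0.78"). The sentence before it describes stopping when the combination is believed to be worse. Table 15 is introduced with a single assumption: "Below are the operating characteristics of the above futility monitoring rule, assuming that the median PFS of the TMZ alone arm is 3 months". No prior, event-time model or assessment schedule is given for it.

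Section 6.3.5 fixes the assessments: "Patients will undergo response evaluations every 2 months". The Study Calendar (3.8) has brain MRI every two cycles, and Section 3.2.2 gives 28-day cycles. PFS runs from registration to progression or death (6.3.8). Progression can also be recorded without a scheduled scan, through death or deterioration (6.3.4) or clinical decline (Appendix 15.5).

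**The concern.** Most PFS events in this trial become known at a scan. A patient enrolled less than 8 weeks before a look cannot yet have a scan-detected progression, and a progression between scans surfaces only at the next one. A simulation that lets every progression be known immediately gives each look more events than the visit schedule can deliver.

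Table 15 is the plan's only quantified evidence on how well PFS futility monitoring limits enrolment to an inferior combination. If it rests on immediate detection, whoever approves the rule is relying on figures that the trial as scheduled would not produce.

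**Working it through.** **Unscanned patients at each look.** At 4 per month the looks fall at months 20/4 = 5, 40/4 = 10 and 60/4 = 15. With a 2-month scan interval, 4 x 2 = 8 patients have had no first scan: 8/20 = 40%, 8/40 = 20%, 8/60 = 13%. With exactly 56 days (56/30.44 = 1.84 months), 4 x 1.84 = 7.4 patients, or 37%, 18% and 12%.

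**Model (assumed, since the plan gives none).** PFS is exponential with hazard ln 2 / median, and the control median is 3 months. Each arm's hazard has a Gamma(a, b) prior, so with d events in total time T the posterior is Gamma(a + d, b + T). Pr(combination median >= TMZ median) is then the probability that the combination's hazard is no greater than the control's, obtained from an F distribution. Accrual of 4 per month covers both arms, looks are at the 20th, 40th and 60th entry, the maximum is 80, and there is no dropout. The prior shown is Gamma(1, 4.33), where 4.33 = 3/ln 2. Each cell uses 20,000 to 40,000 simulated trials; at 20,000 the standard error of a probability near 0.8 is sqrt(0.8 x 0.2 / 20,000) = 0.003.

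**Results** (early stop probability / mean sample size, by combination median):

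| Setting | 1 mo | 2 mo | 3 mo | 4 mo | 5 mo |
|---|---|---|---|---|---|
| Table 15 | 0.999 / 23.7 | 0.812 / 42.1 | 0.374 / 62.6 | 0.170 / 70.9 | 0.097 / 74.7 |
| 0.22, known at once | 0.999 / 23.6 | 0.807 / 42.1 | 0.387 / 61.8 | 0.171 / 71.2 | 0.086 / 75.2 |
| 0.22, 8-week scans, censored at look date | 0.995 / 28.2 | 0.732 / 48.0 | 0.333 / 64.9 | 0.155 / 72.2 | 0.082 / 75.6 |
| 0.22, 8-week scans, censored at last scan | 0.994 / 29.4 | 0.705 / 49.6 | 0.319 / 65.5 | 0.144 / 72.7 | 0.079 / 75.7 |
| 0.22, 40% of events seen at once, rest at scans | 0.997 / 26.6 | 0.755 / 45.9 | 0.348 / 63.8 | 0.160 / 71.8 | 0.085 / 75.3 |
| 0.78 as printed, known at once | 1.000 / 20.1 | 0.996 / 21.9 | 0.932 / 27.5 | 0.797 / 35.3 | 0.654 / 42.9 |
| 0.78 as printed, 8-week scans | 1.000 / 20.1 | 0.998 / 21.4 | 0.964 / 24.9 | 0.875 / 30.3 | 0.773 / 35.7 |

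The second row matches all ten cells of Table 15 within simulation tolerance; a Gamma(2, 4.33) prior does too.

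**What does not reproduce the table.**
- The printed 0.78: 0.932 at equal medians against 0.374.
- Complete follow-up at each look, cut-off 0.22: 0.854 / 36.9 at 2 months and 0.036 / 78.0 at 5 months.
- Scan detection at another cut-off: 0.28 nearly fits the 2-month column (0.799 / 43.4), but then gives 0.423 at 3 months, 0.219 at 4 months and mean N 26.4 at 1 month.

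**Ranges with scan detection at 0.22,** over priors, censoring conventions and 0-40% of events seen at once: 2-month combination 0.70-0.76, mean N 46-50; 1-month combination 0.994-0.997, mean N 27-30. With equal medians, expected events at the first look fall from 7.6 to 5.2.

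**If the medians are documented PFS.** With scans every s = 1.84 months, mean documented PFS is s / (1 - exp(-hazard x s)). Setting it to 2/ln 2 = 2.89 gives hazard x s = -ln(1 - 1.84/2.89) = 1.015. Setting it to 3/ln 2 = 4.33 gives -ln(1 - 1.84/4.33) = 0.554. The underlying hazard ratio becomes 1.015/0.554 = 1.83 instead of 3/2 = 1.5. The 2-month stop probability is then 0.84-0.87 (mean N about 41-43) and the equal-arm figure 0.28-0.32. Keeping the hazard ratio at 1.5 gives 0.68-0.72 at 2 months.

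**The case against.** The strongest objection is about what a median in Table 15 means. Sections 6.3.4 and 3.10.1 tie progression to MRI, so the medians may be medians of documented PFS, with scan delay already inside them. Matched on mean, the 2-month stop probability rises above the printed 0.812 and the apparent overstatement disappears. This stands: the direction of the error depends on a definition that the plan does not give. It does not rescue the table. The equal-arm figure moves from 0.374 to about 0.28-0.32, and with scan-only detection a documented median of 1 month cannot occur, because the first scan is at 1.84 months. Underlying medians of 2 and 3 months both give a documented median at the second scan, 3.68 months.

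Second, the direction also depends on the cut-off. Under the printed 0.78, an inferior combination stops more often and earlier than Table 15 says, even with scan delay. That stands too, and makes the cut-off conflict the larger error.

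Third, the prior and code are not in the documents, and examinations with KPS every cycle (Sections 3.5.1 to 3.5.3) will catch some progressions between scans. Hence the ranges; with 40% of events seen at once the 2-month figure is still 0.755.

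A reader might infer more than this. One inference is that Table 15 ignores immature follow-up at enrolment-triggered looks. It does not: it is reproduced only when that is included. Another is that the looks must be delayed. Pausing 8 weeks before each analysis gives 0.737 / 46.3 at 2 months, so unscanned patients explain only part of the drop; much of it comes from event times being rounded up to scan dates.

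**Conclusion.** Table 15 does not describe the trial as scheduled. It fits a rule with cut-off 0.22 and immediate knowledge of progression, whereas the protocol prints 0.78 and scans every 8 weeks.

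If the cut-off is 0.22 and the medians are underlying progression times, the table overstates the 2-month stop probability by about 6 to 11 points (0.81 against 0.70-0.76) and understates mean enrolment by about 4 to 8 patients. At a 1-month median only the timing changes, by about 3 to 6 patients. If the medians are documented PFS matched on mean, the 2-month figure is understated and the equal-arm figure overstated.

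The documents do not support a general statement that futility protection is overstated: that holds on one reading of the medians and one cut-off, mainly at 2 months. The conclusion rests on exponential PFS, weak priors, accrual of 4 per month for both arms together, no dropout, and an inference from reproducing the table.

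**What to change.** First reconcile the printed 0.78 with the sentence before it and with Table 15, since every figure depends on the cut-off.

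Then re-run and restate Table 15 with progression observed at the 8-weekly evaluations, plus deaths and clinical progression between scans at a stated assumed share. Beside the table, state whether the medians are underlying or documented PFS, the prior, and how patients without an event are censored at a look. Censoring at the last scan is optional: it is a modelling choice, and it lowers stopping at 2 months from about 0.74 to 0.71.

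The cost is one simulation re-run and a revised table, with some less favourable figures. Look timing, visits and enrolment do not change.

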3.10 CRITERIA FOR REMOVAL FROM PROTOCOL THERAPY AND OFF STUDY CRITERIA

3.10.1 Criteria for Removal from Protocol Therapy

- After administration of 12 cycles of treatment, unless there is clear evidence of clinical benefit to justify continuation of treatment based on treating physician's opinion.
- Progressive disease if patient not eligible for or refuses crossover or progressive disease * after crossover to TMZ+ Zotiraciclib (TG02)
- The patient may withdraw from the study at any time for any reason
- Unacceptable Toxicity as defined in section **3.3**
- Investigator discretion
- Treatment related adverse events not resolved within a 4-weeks rest period or requiring more than two dose de-escalations of any drug whichever is earlier.
- Pregnancy

* Delayed imaging responses have been observed in some patients who received protocol treatment. If a patient is clinically stable or clinically improved, even while MRI showed >25% increase in tumor size, the patient may continue on study treatment per P.I. discretion for one additional cycle, at which time a repeat scan will be done. If tumor size continues to increase, disease progression will be dated back to the date of prior MRI.

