6.3.7 Duration of Response

Duration of overall response: The duration of overall response is measured from the time measurement criteria are met for CR or PR (whichever is first recorded) until the first date that recurrent or progressive disease is objectively documented (taking as reference for progressive disease the smallest measurements recorded since the treatment started).

The duration of overall CR is measured from the time measurement criteria are first met for CR until the first date that progressive disease is objectively documented.

Duration of stable disease: Stable disease is measured from the start of the treatment until the criteria for progression are met, taking as reference the smallest measurements recorded since the treatment started, including the baseline measurements.

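### The SAP plans descriptive statistics for response duration and does not say how responders without documented progression are handled, so the reported duration may be too short

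*Combined protocol and SAP*

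**What the plan says.** The Statistical Analysis Plan paragraph in section 10.2 covers the cohort expansion and phase II. It gives the response proportion an exact binomial interval and then will "use descriptive statistics to summarize response duration". The next sentence moves to the other time-to-event outcomes: "We will estimate PFS/OS with the Kaplan-Meier product limit estimator". The log-rank comparison that follows is also for PFS and OS only.

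Section 6.3.7 measures duration from first CR or PR "until the first date that recurrent or progressive disease is objectively documented". It has no rule for a responder in whom that date never occurs.

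Several provisions make such responders likely:

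- Section 3.10.1 ends protocol therapy as follows: "After administration of 12 cycles of treatment, unless there is clear evidence of clinical benefit".
- The off-study visit (3.10.2 and the study calendar) includes no MRI.
- Contact after therapy (3.6) is for survival status.
- Patients may leave the study to start another therapy or be lost to follow-up (3.10.3).
- For phase II, section 10.2 states: "We will follow all patients for at least 12 months".

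**The concern.** A response that is still ongoing when imaging stops, or at data cut-off, has no completed duration. It is a censored time. Descriptive statistics as usually programmed (mean, median, range) have no place for censored times, so the programmer must choose. The ongoing responses can be left out, or their last observed time can be entered as if the response had ended. Leaving them out removes the longest responses. Averaging them as ended cuts them short. The plan decides neither way, and the same paragraph uses descriptive statistics for baseline characteristics, which are fully observed.

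At stake is the credibility of a published figure for how long responses last. The handling could be chosen after the data are seen, and the choice can nearly halve the figure.

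**Working it through.** The documents give no expected response duration, number of responders or censoring rate, so there is no planned figure to reproduce. The check below shows direction and size under stated assumptions.

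**Inputs from the documents**

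- Accrual is "at most 40 patients for each arm at a rate of 4 patients per month" (10.2). That is 80 / 4 = 20 months, so with a 12-month minimum, follow-up runs from 12 to 32 months.
- The treatment limit is 12 cycles of 28 days: 336 days / 30.4375 = 11.04 months.
- On imaging, section 6.3.5 says: "Patients will undergo response evaluations every 2 months".
- The control-arm planning value is given in 10.2: "assuming that the median PFS of the TMZ alone arm is 3 months".

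**Assumptions**

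- Durations are exponential with median M, so the rate is λ = ln 2 / M and the true mean is 1/λ.
- Response is first seen at month 2 or month 4, equally often.
- Scenario A: imaging continues through the 12 to 32 months of follow-up, with uniform entry and no early loss.
- Scenario B: imaging ends at cycle 12 for everyone.

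**Formulas**

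Let c be the proportion censored.

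- A: c is the average over r = 2, 4 of [exp(−λ(12−r)) − exp(−λ(32−r))] / (20λ).
- B: c is the average over r = 2, 4 of exp(−λ(11.04−r)).
- Mean with ongoing responses counted as ended: (1 − c)/λ.
- Median of progressors only: −ln(1 − (1 − c)/2)/λ. This is valid when the result falls before the earliest censoring time, which is 8 months in A and 11.04 − 4 = 7.04 months in B.

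**M = 6 months** (λ = 0.1155, true mean 8.66)

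- A: c = average of (0.3150 − 0.0313)/2.3105 = 0.123 and (0.3969 − 0.0394)/2.3105 = 0.155, which is 13.9%. Mean = 0.861 × 8.66 = 7.45. Progressor-only median = 4.88.
- B: c = average of 0.352 and 0.443, which is 39.8%. Mean = 0.602 × 8.66 = 5.21. Progressor-only median = 3.10.
- The simple median of all responders, with censored times kept as observed, is 6.0 in both. No censoring falls before 7.04 months, so half the observed times still lie below 6.

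**M = 3 months** (λ = 0.2310, true mean 4.33)

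- A: c = 2.7%. Median of all responders 3.0, progressors only 2.9, mean 4.2.
- B: c = 16%. Median of all responders 3.0, progressors only 2.4, mean 3.6.

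**M = 9 months** (true mean 13.0)

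- A: c = 25.5%. Median of all responders 8.7, progressors only 6.0.
- B: c = 54%. Median of all responders 7.0, progressors only 3.4.

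**Early loss.** With 20% censored per year added to A at M = 6, the extra hazard is −ln(0.8)/12 = 0.0186. The simple median of all responders falls to 0.6931/(0.1155 + 0.0186) = 5.2 months. In simulation, 23% are then censored.

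A simulation of 400,000 responders agrees with these values. In it the Kaplan-Meier median returned the assumed median wherever it was reached. It was not reached at true medians of 12 and 18 months when imaging ended at cycle 12.

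**The case against.** The strongest reply is that the plan is silent rather than wrong. Descriptive statistics can include a Kaplan-Meier median, or a listing with ongoing responses flagged. A reader might infer that the plan commits to simple means and that the reported duration is therefore certain to be short. The text does not say that: it names no mean, no exclusion of ongoing responses and no counting of them as ended. This stands, and the point is conditional for that reason.

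A reader might also infer that both ways of handling ongoing responses shorten any summary. They do not. The simple median of all responders is unaffected while censoring falls after the true median, which covers true medians up to about 6 months without early loss.

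The protocol's own figures point towards shorter durations: a control median PFS of 3 months, values of 1 to 5 months for the combination in Table 15, and observed PFS4 of 38% and 25%. Responders may last longer than the average patient, but no document says by how much. Scenario B is also an extreme, since 3.2.2 and 3.10.1 allow treatment past cycle 12 where there is clinical benefit, and a patient still in response is an obvious candidate. These points limit the size. They do not supply the missing rule.

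Finally, duration is not the only record of how lasting responses are. Section 6.3.6 classifies each response as sustained or non-sustained at the next scheduled MRI. Duration is the only planned measure on a time scale.

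**Conclusion.** The gap is real and its impact is modest. Section 10.2 gives a censored outcome no method that handles censoring, although it names one for PFS and OS in the next sentence, and section 6.3.7 gives no rule for responders without documented progression.

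If ongoing responses are dropped or averaged as ended, the error is towards too short. At a true median of 6 months, the progressor-only median is about 3.1 to 4.9 months and the mean about 5.2 to 7.5 against 8.7, with about 14% to 40% censored. With durations near 3 months and full follow-up it is negligible. These figures rest on exponential durations, onset at month 2 or 4, and the two imaging scenarios. None of these assumptions is a figure given in the documents.

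A reader might go further and conclude that the comparison between arms is biased against the better arm. The documents do not support that as a flaw in a planned analysis. The SAP plans no test of response duration between arms, duration is not among the objectives in 1.1.2, and no stopping, dose or schedule decision uses it.

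**What to change.** In section 10.2, replace "use descriptive statistics to summarize response duration" with wording such as: *estimate duration of response by the Kaplan-Meier method, censoring responders without an event at their last tumour assessment, and report the number of responders, the number censored and the median with 95% CI by arm.*

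The event must be defined at the same time. Section 6.3.7 ends a response at documented progression and does not mention death. Section 6.3.4 counts failure to return because of death as progression, and 6.3.8 counts death as a PFS event. The three sections should be aligned on whether death ends a response. Writing progression or death into the SAP alone would contradict 6.3.7.

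The cost is one SAP sentence and one definitional alignment, with no new data. With few responders the median may be imprecise or not reached. In that case the number of responders and the number censored still show the reader how much has been observed.
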